#### 4.6.3 *Exploratory Endpoints*

- Transepithelial water loss at weeks 2, 3 and 4
- Wound pain VAS at time of first dressing change and day 10 and weeks 2, 3 and 4
- Pruritis VAS at weeks 3, 4, 8, 12, 26 and 52
- Patient and Observer Scar Assessment Scale (v2.0) weeks 3, 4, 8, 12, 26 and 52
- Skin elasticity (Delfin Elastimeter) measurement at 12, 26 and 52 weeks
- Vancouver Scar Scale at 12, 26 and 52 weeks
- Skin pigmentation (Delfin SkinColorCatch) measurement at weeks 12, 26, and 52
- Skin hardness (Delfin Skin Fibrometer measurement) at weeks 12, 26, and 52
- Biomarkers related to burn injury (such as C-reactive protein (CRP), IL-6, IL8, IL1 $\beta$ , interleukin-1 receptor antagonist (IL-1ra); neutrophil gelatinase-associated lipocalin (NGAL); Tumor Necrosis Factor- $\alpha$  (TNF $\alpha$ ), and tumor necrosis factor receptor 1a (TNFR-1a)) and related to scarring (such as amino-terminal propeptide of type III procollagen, (PIIINP), TIMP1, MMP2, MMP9 and VEGF-A) will be collected at baseline (prior to treatment), days 6, and 10 and weeks 2, 3, 4, 8 and 12 post ADRC administration. Serum sample will be collected from 4 to 5 ml of whole blood that is centrifuged, separated into 500- $\mu$ L aliquots, and stored at -80°C at the clinical site serum bank or central lab until use.
- Serum biomarkers will be measured using commercial Enzyme-Linked ImmunoSorbent Assay (ELISA).

### 4.7 Inclusion and Exclusion Criteria

#### 4.7.1 *Inclusion Criteria*

Subjects will be enrolled into this study only if they meet ALL of the following criteria:

1. Males or females,  $\geq 18$  to  $\leq 65$  years of age
2. BMI  $> 20$  kg/m^2
3. Burn TBSA 20% - 50%
4. At least one deep partial thickness and/or full thickness thermal burn  $\geq 250$  cm^2 on the arms, legs, back, abdomen or chest that is anticipated to be covered with a meshed autologous STSG and that has not been treated previously with a biologic dressing such as Alloderm® or Integra®
5. Ability to safely undergo adipose tissue harvest procedure that is anticipated to yield  $\geq 150$  mL of adipose tissue at a site that is free from infection
6. Donor site availability for skin graft harvest

7. Able to provide written informed consent, signed by either the patient or their legally authorized representative
8. Women and men of child-bearing potential agreeing to use contraception during the study. Acceptable methods include surgical sterility, IUDs, hormonal contraception or double barrier methods.

#### **4.7.2 Exclusion Criteria**

Subjects will not be enrolled into this study if they meet ANY of the following criteria:

1. Burn > third degree (i.e. involvement of deeper tissues, such as muscle, tendon, or bone)
2. Subjects with electrical or chemical burns
3. Subjects with significant inhalation injuries necessitating intubation and mechanical ventilation or requiring > 50% FIO₂ on a continuous basis to maintain oxygenation (O2 sat > 90%)
4. In the opinion of treating physician, patient not to be expected to survive beyond 30 days
5. Pre-existing condition requiring current use of immunosuppressive medication or systemic steroids
6. Pregnant or lactating. Pregnancy as determined by a positive pregnancy test at screening or baseline
7. Known history of HIV infection, or has active Hepatitis B or active Hepatitis C infection.
8. Cancer requiring chemotherapy or radiation within previous 6 months or resection within the last 5 years (other than basal cell carcinoma)
9. Known chronic renal failure (serum creatinine > 2 mg/dL) or chronic liver disease
10. Pre-existing medical conditions that would interfere with wound healing (i.e., diabetic patients with Hemoglobin A1c  $\geq$ 8.0%, malignancy, autoimmune disease)
11. Subjects with psychiatric conditions that are anticipated to result in protocol noncompliance
12. Chronic illicit drug or alcohol use that is anticipated to interfere with patient compliance to the protocol
13. Participation in another clinical trial within 60 days of screening visit
14. Any concurrent disease or condition that, in the opinion of the investigator, would make the patient unsuitable for participation in the study

## **5 ENROLLMENT**

### **5.1 Subject Enrollment**

Subjects are considered enrolled in this study when all of the following have occurred:

1. Written informed consent is obtained
2. All inclusion criteria and no exclusion criteria have been met
3. All screening evaluations are complete
4. Commencement of fat harvest (except for usual care control subjects who will not undergo a lipoaspirate procedure)

## 5.2 Randomization and Subject Identification

Randomization to ADRC and usual care will occur within 2 hours prior to the scheduled surgery for STSG.

Randomization will be done via an interactive web response system (IWRS). Subjects will be randomized in a 2:1 ratio to receive intravenous delivery of either Celution® System processed ADRCs with usual care or to usual care alone.

A total of up to 15 subjects will be enrolled. Each patient will contribute up to three qualified wound areas for the analysis. If more than one wound is identified, each must be noncontiguous with the other(s). Therefore, between 15 and 45 wounds will be evaluated.

The 1st 5 subjects enrolled in active treatment will be observed for adverse events over a 7 day period. If no SAEs occur during that period, for that individual subject, the next subject enrolled in active treatment may be entered with the same 7 day observation period. The safety results of the first 5 subjects will be reviewed by the DMC and their evaluation will be used in conjunction with the clinical data collected to date, and if appropriate, to potentially remove the staggering approach to the study. Enrollment after the first 5 subjects enrolled in active treatment may continue only after the DMC has completed its safety review and recommends continuation.

## 5.3 Stopping Rules

The study will be stopped and patient enrollment will be suspended if any of the following events occur:

1. Acute cardiovascular adverse event occurring within seventy-two (72) hours of the ADRC infusion.
2. Acute allergic or anaphylactic response within seventy-two (72) hours of the ADRC infusion.
3. Acute pulmonary adverse events such as acute respiratory distress syndrome (ARDS) and renal adverse events such as acute renal failure (ARF) within seventy-two (72) hours of the ADRC infusion.

The Sponsor will notify the DMC and FDA immediately for their review and recommendation on study continuation.

## 5.4 Blinding Procedures and Safeguards

The “blinded party” (photographic assessor(s) with no knowledge of the subjects treatment assignment) are those involved in the independent evaluation of the wound digital photographs.

All others involved in the study are considered the “unblinded parties”, meaning those that will or may have knowledge of a patient’s treatment assignment.

## 5.5 Subject Withdrawal and Replacement

Subjects may withdraw from the study at any time and for any reason without penalty or prejudice to his or her future medical care. If a subject is prematurely withdrawn from the study for any reason, the reason(s) for withdrawal must be recorded in the Subject’s source documentation and on the eCRF.

The Investigator must make every effort to perform the Early Termination evaluations. This visit shall take place as soon as possible after it is determined that the Subject will be withdrawn from the study and will comprise the observations and procedures scheduled at the next visit.

## 6 CELUTION® SYSTEM

### 6.1 Celution® System Description

The Celution® System consists of a stand-alone re-useable hardware unit called the Celution® 800/IV Device with v5.1 firmware with Heater Attachment accessory, the Celution® 805/IV Consumable Set, Celase® and Intravase®. The Celution® System prepares an ADRC output from adipose tissue collected by standard syringe aspiration techniques. The tumescent fluid is composed of: 500 mL of lactated Ringers solution, 20 mL of 1% lidocaine, and 1mg of epinephrine.

Following the collection and preparation of tissue via fat harvest, the adipose tissue is introduced into the device's collection canister in order to wash the adipose tissue and remove deleterious substances (such as cellular debris) (Detailed instructions for use are found in the *Celution® User Manual*).

### 6.2 Device Characterization and Intended Use

The Celution® 800/IV Device is intended to be used in conjunction with the Celution® 805/IV Consumable Set, Celase and Intravase to digest human adipose tissue in order to further extract, wash, and concentrate adipose derived regenerative cells intended for autologous reinfusion (intravenous) for burn wounds for investigational use in the RELIEF clinical trial.

### 6.3 Contraindications

1. Non-autologous use
2. Use of any tissues other than adipose

### 6.4 Intended Clinical Performance

The Celution® System is designed to process lipoaspirated tissue to separate ADRCs from adipose tissue by enzymatic disassociation of the tissue and using buoyancy differences and centrifugation to separate and then concentrate the ADRCs from lipid containing adipocytes. When ADRCs are prepared using the Celution® System, the resultant cell suspension contains all of the components naturally occurring in the native tissue. Preparation of autologous ADRCs for delivery using the Celution® System involves no cell culture. The prepared ADRC dose can be administered to the same patient within four hours.

A percentage viability of  $\geq 70\%$  of the ADRC output will be used as the acceptance criteria.

The total viable cell count will be performed using a validated system that counts both viable and non-viable nucleated cells (NucleoCounter NC-100® Automated Cell Counting System). This count is used to calculate the total number of live nucleated cells from the entire preparation, to arrive at a quantity of viable cells for treatment of the patient.

### 6.5 Celution® System Output: Physical, Chemical, and Mechanism of Action

The product of the Celution® System is an ADRC output obtained from autologous lipoaspirate. The suspension of viable ADRCs has been characterized with a average viability of  $>70\%$  and the average

yield is  $3.22 \times 10^5 \pm 1.48$  cells per gram of adipose tissue processed in the Celution® System. An index of regenerative cell potential, the CFU-F assay, shows that 1.51% of those ADRCs form colonies (mean range of 0.13 to 4.08% colony forming units).

The product is a suspension of cells in a diluent. The cellular components of the suspension are made up of nucleated and non-nucleated cells. The non-nucleated cells are red blood cells (RBC) that comprise > 95% of the total cell suspension. The nucleated cells make up approximately 0.1 – 5% of the total cell suspension.

The combination of these four phenotypes will account for approximately 90% of nucleated cells in the product. Table 1 summarizes the ADRC cellular suspension processed by the Celution® System.

**Table 1. ADRC cellular suspension components and concentrations**

Cell Type	Phenotype	Relative Identity of Nucleated Cell Population
Non-nucleated Cells	Red Blood Cells	
Endothelial Cells	CD45-, CD31+, CD34+	> 2%
Stromal Cells	CD34+, CD31-, CD45-	> 5%
Leukocytes	CD45+, CD31-, CD34-	> 5%
Mural Cells	CD45-, CD34-, CD 31-, CD146+	> 2%

## 6.6 Proposed Mechanism of Action of ADRCs

The proposed mechanism of action of the ADRCs prepared with the Celution® System is postulated to be modulation of inflammation, promotion of angiogenesis and prevention of cell apoptosis. Studies suggest that ADRC therapy changes the inflammatory response and augments the regenerative response starting early in the injury process. Studies have detected significant amounts of paracrine growth factors, which have been shown to facilitate vascularization, and factors associated with anti-inflammatory effects, thereby ameliorating injury by pro-inflammatory cytokines. This has been demonstrated to repair healing impaired, deep, and chronic wounds. Viability characterization of ADRCs as described above, in addition to pre-clinical animal data from Cytori and other published reports, support this hypothesis.

## 7 STUDY TREATMENTS

Subjects randomized to ADRCs will receive active treatment (intravenous infusion of  $20 \times 10^6$  ADRCs into a peripheral vein). Subjects randomized to the control group will not undergo fat harvest and not receive any study treatment. All subjects will continue their usual care treatment.

### 7.1 Product Description - ADRCs

Lipoaspirate will be obtained through a low volume lipoharvest (100-150 mL) which will be performed at the start of general anesthesia for the scheduled burn surgery. The lipoaspirate will be processed using the

Celution® System to produce ADRCs. The ADRCs will be delivered via intravenous approximately within 4 hours of Celution processing.

The adipose tissue is introduced into the device's collection container in order to wash and process the tissue. Based on a fat harvest of 100-150 mL, the expected cell output would be approximately 20 to 40 million cells. The target dose for the study is 20 million cells.

The excipients in the cell suspension are composed of residual Celution® System reagents and diluent. Specifically, the residual reagents are collagenase (<0.005 Wünch Units/mL) and DNase (<100 Kunitz Units/mL). The diluent is Lactated Ringers solution (USP).

Adipose tissue processing is detailed in the *Celution® System Users Manual*. Preparation of the active study treatment is provided in the *Study Reference Manual*.

### **7.1.1 Treatment Dose Control**

ADRC count and viability will be determined using a validated system that counts both viable and non-viable nucleated cells (NC-100 NucleoCounter® Automated Cell Counting System, Enfield, Connecticut, USA) using the following criteria:

- Nominal cell count:  $20 \times 10^6$  ADRCs
- A minimum cell count within 15% of the nominal cell count is required (i.e., a dose as low as  $17 \times 10^6$  ADRCs is acceptable if  $20 \times 10^6$  ADRCs is not available)
- Cell viability:  $\geq 70\%$
- If cell viability is  $< 70\%$ , as determined by the NucleoCounter® Automated Cell Counting System, the subject will not be treated but will be followed per study protocol for safety.
- Negative result in Gram stain testing (see *Section 7.2*)
- If the Gram stain testing result is positive, the subject will not be treated but will be followed per study protocol for safety.

### **7.2 Study Treatment Sterility Testing**

Following cell processing in the Celution System sterility testing will be performed as described below and more fully in the *Study Reference Manual* and the *Cell Preparation Manual*.

[figure not shown]
A negative Gram stain test result is required prior to injections of ADRCs. If the sample is determined to be positive for bacteria then the subject should not receive any study treatment, but will be followed per study protocol for safety.

Further testing (aerobic bacteria culture (e.g. BacT Alert or BacTec)) will be performed in order to test for the presence of any low level microbial contamination that might not be apparent in the gram stain test. Should a culture be deemed positive for microbial activity, the investigator will be immediately notified. The study patient will be evaluated and a course of treatment and/or antibiotics may be administered, as determined by the study investigator. The source of the contamination will be evaluated as appropriate. If the culture test indicates potential bacterial contamination of the study treatment and the clinical follow up

indicates potential or actual infection of the subject, the FDA and IRB will be notified within 15 days of the Sponsor being made aware of any positive test results.

The following flow chart describes the activities associated with positive or negative outcomes in these two tests of sample sterility.

**Figure 1: Sterility Testing of ADRC Samples**

### 7.3 ADRC Characterization

Additional ADRC phenotypic characterization beyond the cell counting and bacterial testing required for dose preparation may be performed for subjects for whom ADRCs in excess of the number needed for dosing, cell counting, and bacterial testing are available. Such testing should be performed according to methods developed by Cytori. Flow cytometry methods will be used to determine ADRC cellular composition. Particularly, detailed characterization will be performed on left over cells once the cell dose preparation has been prepared for the injection procedure. Within the ADRC population, cells will be identified phenotypically by combination of the following markers: CD45, CD34, CD31 and CD146.

Once the cell dose is prepared according to criteria described in *Section 7.1.1*, any excess ADRCs may be stained and fixed at the clinical site using antibodies directed to CD31, CD34, CD146 and CD45 proteins according to instructions in the *Study Reference Manual (Cytori Work Instruction)*. Samples will be then shipped to the testing facility within 92 hours.

Based on the expression of these four markers, the major populations will be defined as follow:

Leukocytes	CD45+
Endothelial Cells	CD34+/CD31+/CD45-
Stromal Cells	CD34+/CD31-/CD45-
Mural cells	CD34-/CD31-/CD45-/CD146+

Other markers (such as CD206, CD14, CD90, CD73, CD105 and CD44 or other related markers) may be used to further characterize ADRCs subpopulation.

## 8 STUDY ASSESSMENTS

All parameters will be conducted at specific time points as outlined in this section. As a reference point during the study, a Schedule of Procedures is provided in *Appendix A*.

### 8.1 Medical History, Physical Examination & Vital Signs

A complete medical history will be collected at Screening and will include demographic information, current and past medical conditions and a summary of the burn event. Any adverse event that occurs after the ICF is signed and prior to the fat harvest is to be recorded as an update to the Medical History.

Physical examinations should be based on the following body systems: general appearance, head (ear, eyes, nose and throat), respiratory, abdomen, musculoskeletal, neurological, and skin, including total burn surface area (TBSA) on admission, percent of third degree burns, and other trauma related to the burn event. Vital signs to be obtained include the following:

- Blood pressure (systolic and diastolic; mm/Hg)
- Heart rate (beats per minute)
- Body temperature (°C)
- Respiration rate (per minute)

### 8.2 Adverse Events

Adverse events will be assessed throughout the study according to the NIH Common Terminology Criteria for Adverse Events (CTCAE) v4.0 for scale grading adverse events.

### 8.3 Burn Evaluations

The physical characteristics of the selected burn areas and the graft (up to 3 per subject) as well as the subjective evaluation of symptoms will be evaluated using several assessment tools. The assessment tools are listed below and detailed information and instructions provided in the *Study Reference Manual*. Planned study days are listed below but an acceptable range of days (±) is in the schedule of events.

- Percent epithelialization at early dressing changes (estimated time of first dressing change and day 10 after graft application and at weeks 2, 3 and 4 (by surgeon evaluation and blinded independent review of standardized photographs)
- Percent take of the graft at early dressing changes (estimated time of first dressing change and day 10 after graft application (if wound dressing must be changed) and at weeks 2, 3 and 4
- Occurrence of complete wound healing at each assessment weeks 4 to 12
- Transepithelial water loss at weeks 2, 3 and 4
- Wound pain VAS at time of first dressing change and day 10 and weeks 2, 3 and 4
- Pruritis VAS at 3, 4, 8, 12, 26 and 52 weeks
- Patient and Observer Scar Assessment Scale (POSAS) at 3, 4, 8, 12, 26 and 52 weeks
- Vancouver Scar Scale at 12, 26, and 52 weeks
- Skin elasticity measurement at 12, 26 and 52 weeks (Delfin SkinElastimeter)
- Skin pigmentation (Delfin SkinColorCatch) measurement at weeks 12, 26, and 52
- Skin hardness (Delfin SkinFibrometer) measurement at weeks 12, 26, and 52

- Percent of wounds with complete wound closure at weeks 2, 4, 8 and 12
- Digital photography of treated wounds on day 1 and each follow up visit
- Biomarkers related to burn injury will be assessed from 4-5mL blood (serum) samples drawn at baseline (prior to treatment), time of first dressing change and day 10 and weeks 2, 3, 4, 8 and 12 post-ADRC administration.

## 8.4 Prior and Concomitant Medications

Any medication a subject receives is considered a concomitant medication, and must be recorded in the subject's source documentation throughout the study. All concomitant medications will be recorded in the eCRF starting at screening through the 52 week visit. Information to be recorded on the eCRF will include: generic medication name, route of administration, dosage, indication, start date, and stop date.

Medications used as part of the tissue harvest procedure and the escharectomy/grafting surgeries do not need to be recorded in the eCRF but should be recorded as part of the operative records.

### 8.4.1 Prohibited Medications

Subjects should not receive the following medications for the duration of the study:

- Any other investigational drug or agent
- Any chemotherapy or immunosuppressive medication
- Systemic steroids exceeding prednisone 10 mg daily (or equivalent) for periods exceeding 4 weeks
- Any anticoagulant administered for systemic anticoagulation that would contraindicate a lipoaspiration procedure. Subcutaneous heparin or low molecular weight heparin for deep vein thrombosis prophylaxis is acceptable
- A substantial anticoagulant such as a Glycoprotein IIb/IIIa inhibitor/anti-platelet class drug was administered within 2 weeks prior to fat harvest (such as ReoPro, IntegriLin or Aggrastat)

If treatment with any prohibited medication becomes necessary during study participation, the subject will be followed; however, the subject would not be included in the PTE population.

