#### **4.5 Study Duration**

Enrollment is anticipated to be completed over 18 months. For each patient, the study duration will include a 12 month follow-up period. The total duration of the RELIEF Trial is estimated to be 30 months.

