## **9.4 Intravenous Delivery Risk Analysis and Management**

Risks involved with intravenous delivery of ADRCs cells include:

- Embolism
- Infection

The preclinical studies described herewith demonstrate no evidence of serious adverse events associated with ADRCs delivered intravenously, topically, subcutaneously, or intraarticularly. The clinical trial studies also have not reported significant safety issues when ADRCs are delivered subcutaneously, intraarticularly or intra-arterially. As in other trials applying intravascular administration of ADRCs, the ADRC product will be passed through a 47 $\mu$ m filter as part of the infusion process in order to further minimize risk of embolism. However, the possibility of infection exists with any percutaneous procedure. However, current experience in multiple clinical studies has not revealed any patient infections association with ADRCs delivery.

To mitigate potential risk of infection a gram stain of the ADRCs doses will be performed and must be negative in order to proceed with intravenous administration. A sample will be sent to the hospital laboratory for BacT (or equivalent) culture including aerobic microorganisms and sensitivity. All procedures related the Celution® System and cell counting are performed in aseptic conditions. If a culture result is positive for microbial activity, the investigator will be immediately notified. The study patient will be evaluated and standard clinical treatments of infection for patients with burn wound injury should be followed including antibiotics as deemed appropriate by the study investigator.

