## 10 STATISTICAL METHODS AND DATA ANALYSIS

The RELIEF Trial is a multi-center, open-label, randomized, usual care controlled study to evaluate the feasibility and safety of ADRCs with usual care compared to usual care alone in subjects with thermal burns. The primary endpoint will be safety and feasibility.

The ITT population will be used for the primary analysis; the analysis will also be presented in the PTE population.

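### As written, the prohibited-medication exclusion from PTE is not limited to efficacy, so an adverse event treated with such a drug could drop out of the PTE safety display

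*Protocol*

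**What the plan says.** Section 8.4.1 opens its list with "Subjects should not receive the following medications for the duration of the study". One item reads "Any anticoagulant administered for systemic anticoagulation that would contraindicate a lipoaspiration procedure", followed by a single exemption: "Subcutaneous heparin or low molecular weight heparin for deep vein thrombosis prophylaxis is acceptable". The section ends by saying that a subject who comes to need a listed drug is followed, but "the subject would not be included in the PTE population". Section 4.5 sets the length of participation: "For each patient, the study duration will include a 12 month follow-up period".

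Section 10 makes ITT the primary population and adds that "the analysis will also be presented in the PTE population". Under 4.6.1 and 10.3.1 the primary endpoint is safety and feasibility. Safety there means adverse events related to the infusion and to the lipoharvest.

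The PTE definitions themselves, in the protocol summary and in 10.5, ask only for early follow-up information (day 6 in the summary, day 5 in 10.5). Neither mentions medication.

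Two risk sections bear on the point. Section 9.4 introduces its list with "Risks involved with intravenous delivery of ADRCs cells include" and puts embolism first. Section 9.6 lists deep vein thrombosis among the rare risks of fat harvest.

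**The concern.** An analysis set used for safety should not depend on whether a safety event happened. Here the route is: procedure, then clot, then systemic anticoagulant, then removal from PTE. The event leaves the numerator and the subject leaves the denominator. Events treated this way would have a PTE rate of zero by construction.

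Harvest and infusion happen only in the ADRC arm (Section 7), so loss from this cause falls on that arm alone. Section 9.10 concedes that the safety of liposuction in burn patients is not established. A second table that looks cleaner than the first could be read as corroborating a benign profile when it only reflects the selection rule.

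**Working it through.** The plan gives no figure to reproduce: the study is not powered (10.2) and no clot rate is stated. The check is a reading of the text followed by an illustration.

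**Step 1. Does the rule reach safety?** Section 8.4.1 excludes the subject from PTE without naming a type of analysis. Section 10 repeats the primary analysis in PTE, and the primary endpoint includes safety. Read together, the exclusion reaches the PTE safety display. Section 10.3 shows that the protocol can draw the distinction. Subjects harvested but not infused because the cells fail release are analysed separately for safety, and they are left out of PTE for efficacy only. Section 8.4.1 has no such limit.

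**Step 2. Does the anticoagulant item apply after harvest?**

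| Points to yes | Points to no |
|---|---|
| The lead-in covers the whole study | The item is qualified by a contraindication to lipoaspiration, which takes place once, on Day 1 |
| The closing sentence concerns need arising during participation | The other anticoagulant rules (8.7.1.1, 9.6.1) concern the time before harvest |
| The next item carries an explicit two-week pre-harvest limit; this one does not | |
| The exemption covers prophylaxis only, not treatment of an established clot | |

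The text supports the first reading but does not settle it. Steps 3 and 4 assume that reading.

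**Step 3. Size if an event occurs.** Inputs: up to 15 subjects (4.3) and 2:1 allocation (5.2), so 15 × 2/3 = 10 active and 5 usual care. Let k active subjects have a clot treated with systemic anticoagulation. ITT shows k/10 and PTE shows 0/(10 − k). Intervals are exact 95% (Clopper-Pearson). For zero events the upper limit is 1 − 0.025^(1/n).

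| k | ITT | PTE |
|---|---|---|
| 1 | 1/10 = 10% (0.3% to 44.5%) | 0/9 = 0% (0% to 33.6%) |
| 2 | 2/10 = 20% (2.5% to 55.6%) | 0/8 = 0% (0% to 36.9%) |

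Check for k = 1: 1 − 0.025^(1/9) = 0.336.

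**Step 4. Chance that it matters.** The probability p of such a clot per active subject is an assumption. The chance of at least one exclusion among 10 is 1 − (1 − p)^10.

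| Assumed p | Chance of at least one |
|---|---|
| 1% | 10% |
| 5% | 40% |
| 10% | 65% |
| 20% | 89% |

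The documents do not say where in this range the truth lies. Listing deep vein thrombosis as rare points to the low end, but that list describes small-volume liposuction in healthy patients.

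**The case against.** The strongest reply is that nothing is lost where it counts. ITT is primary and contains every randomised subject. The excluded subject is still followed. The DMC receives all safety data (10.8), serious events go to the sponsor within 24 hours (11.2), and the stopping rules (5.3) do not refer to PTE. All of this stands, and it confines the problem to a supportive table that sits beside an ITT table showing the event. A reader might infer that the primary safety result is biased; the documents do not support that.

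The second reply is that the lipoaspiration qualifier makes the anticoagulant item a pre-harvest rule, so treating a later clot would never trigger it. That reading is possible, and the point about clots is therefore conditional.

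The third is that the clot link is thin. Section 9.4 offers a 47 µm filter as the mitigation for embolism, which suggests particles or cell aggregates and not necessarily a clot that would be anticoagulated. Deep vein thrombosis is the firmer example.

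The fourth is that use of PTE for safety rests on one general sentence in Section 10. It does, but that sentence is explicit, and 8.4.1 has nothing to offset it.

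Two further readings go too far. One is that any listed drug at any time in 52 weeks removes a subject. The glycoprotein IIb/IIIa item is limited to two weeks before harvest, and steroids count only above a stated dose and duration. The other is that a drug started late in follow-up wrongly discards earlier wound data. Dropping a whole subject from a per-protocol-type set is a common convention, and those data remain in ITT, so this is a matter of preference and not an error.

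**Conclusion.** The point holds in a limited form. Sections 8.4.1 and 10 together allow an adverse event, through its treatment, to remove its own subject from a planned display of the primary safety endpoint. The PTE definitions in the summary and 10.5 do not carry the exclusion that 8.4.1 imposes, so PTE membership is not settled.

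If one treated clot occurred among 10 active subjects, the PTE table would show 0/9 where ITT shows 1/10. This rests on three assumptions: that the anticoagulant item continues after harvest, that 8.4.1 adds to the other PTE definitions, and that such an event happens at all. The effect is on the supportive presentation only. It is worth correcting because the wording is already fixed in the protocol and the correction is nearly free.

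**What to change.** 1. Reconcile 8.4.1 with the PTE definitions in the summary and 10.5, so that one definition states whether medication use excludes a subject.
2. State that the prohibited-medication exclusion applies to PTE efficacy analyses only, following the pattern 10.3 already uses for harvested but untreated subjects.
3. Present safety in all randomised subjects or by procedure received (harvest started; infused), regardless of later medication.
4. Have the sponsor clarify whether the anticoagulant item applies after harvest. This review takes no position on the clinical rule.

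The cost is a small change of wording. No new data are needed and no clinical rule changes. The downside is that the supportive safety table may look slightly less favourable.
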